7.4.1.2 Recording and Assessing Adverse Events

All adverse events, whether reported spontaneously by the patient, in response to open questioning on treatment days or observed by the Investigator or his/her staff, will be recorded from informed consent until the telephone follow-up. The start and stop time will be recorded and adverse events will be assessed by the Investigator for the following:

7.4.1.2.1 Severity

Mild: Resolved without treatment.

Moderate: Resolved or was tolerated with specific treatment without affecting study activities.

Severe: Did not resolve or was not tolerated with treatment.

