4.4 Removal of Patients from the Study

4.4.1 *Screen Failures*

All patients who provide informed consent but for whatever reason are not randomized will be considered a screen failure, and recorded as such in the Interactive Response Technology system (IRT).

The following information will be recorded in the IRT for screen failures:

- Date of Visit 0
- Date of Visit 1 and/or Visit 2 (depending on when the patient screen fails)
- Patient identification number
- Reason for screen failure

For all screen failures who experience an adverse event, and for those who perform at least one screening assessment at Visit 1, eCRFs will also be completed (the IRT system will provide a prompt for this purpose). The information to be recorded is as follows:

- Same information as entered into IRT (per above)
- Adverse events (if any)
- Demographic information including race, age and gender*
- COPD medications taken within 3 months prior to Visit 1*

*These items will only be collected for screen failures for whom at least one screening assessment is performed at Visit 1.

Patients will be stratified based on reversibility at Screening. Each stratum will be capped at 50% of total patients; therefore, when one of the reversibility strata is capped, additional patients meeting the criteria for that stratum will become ineligible for the study and will be considered screen failures.

Patients who screen fail may be considered for re-Screening upon consultation with the Medical Monitor. Re-Screening in the event of failure to meet lung function criteria will generally not be allowed unless extenuating circumstances exist. Repeat, rescheduled, and unscheduled visits and procedures are permitted at the discretion of the Investigator (rescheduled visits are subject to the ± 1 day window mentioned above).

4.4.2 *Study Treatment Discontinuation*

Study treatment must be discontinued for the following reasons:

- Unacceptable toxicity related to study treatment
- Intolerable or persistent adverse events of any severity
- General or specific changes in the patient's condition rendering the patient unacceptable for further treatment in the judgment of the Investigator
- Clinically significant progression of disease
- Pregnancy in a female patient

4.4.3 *Patient Withdrawal*

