7.4.1.2.2 Chronicity

Single occasion: Single event with limited duration.

Intermittent: Several episodes of an event, each of limited duration.

Persistent: Event which remained indefinitely.

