7.4.1.2.4 Action and Outcome

- Action taken with study medication (none, study medication stopped, study medication temporarily interrupted)
- Other actions (none, concomitant medication, study discontinuation, hospitalization, other)
- The outcome and date of outcome according to the following definitions:
 - Recovered or resolved (adverse event disappeared)
 - Recovering or resolving (patient is recovering)
 - Not recovered or not resolved (adverse event remains without signs of improvement)
 - Recovered or resolved with sequelae (adverse event has resulted in permanent disability or incapacity)
 - Fatal
 - Unknown (only applicable if patient has been lost to follow-up)

- Seriousness (yes or no)

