Safety data including laboratory safety tests, 12-lead ECG, vital signs and physical examinations, will be summarized by treatment group and time point of collection, when appropriate, for each of the two parts separately. For continuous variables, the change from baseline (pre-dose at Visit 2) to each post-dose time point will also be calculated and summarized. Data will further be illustrated by shift tables (showing changes from low/normal/high) and shift plots for selected time points. Separate listings will be generated of abnormal values occurring after the first dose of study treatment.

Coded adverse event terms will be presented by system organ class (SOC) and preferred term and summarized by treatment group for each part. Summary tables by treatment group with total number and number of patients with adverse events, SAEs, adverse events leading to discontinuation of study treatment, causally related adverse events and severe adverse events will be produced. Further SAEs, causally related adverse events and adverse events of each intensity will be summarized by SOC and preferred term.

9.4.8 *Handling of Withdrawals or Missing Data*

Imputation of data for calculation of average (AUC) effects for FEV₁ and FVC will be described in the statistical analysis plan. No other imputation of missing data will be performed for the parameter computations. For the sensitivity ANCOVA analyses, missing data will be imputed using the last observation carried forward method prior to analysis.

All available data from all dosed patients who have received study treatment will be listed and summarized. Any unscheduled or unplanned readings will be presented within the patient listings, but only the scheduled readings will be used in any summaries.

9.4.9 *Interim Analyses*

No formal, unblinded interim analysis is planned for the study. To assess the plausibility of the assumptions in the sample size calculation, an estimate of the standard deviation of peak and AUC_{0-3h} FEV₁ will be made based on blinded data after completion of 125 patients. If the estimated standard deviations are markedly higher than the 200 mL assumed (>20%), a revised sample size estimation using the new standard and the previously used detectable difference (89) will be made. If the outcome is an increase of the sample size, an amendment will be submitted for approval.

9.5 *Determination of Sample Size*

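### Adverse event severity is graded mainly by resolution and treatment, so the planned severity tables by dose would not show intensity, and some events fit no grade

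*Protocol*

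**What the plan says.** Protocol 7.4.1.2.1 gives three grades:

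- The lowest is worded "Mild: Resolved without treatment".
- The middle one is worded "Moderate: Resolved or was tolerated with specific treatment without affecting study activities".
- The highest is worded "Severe: Did not resolve or was not tolerated with treatment".

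The neighbouring sections record related facts in separate fields. Chronicity (7.4.1.2.2) includes "Persistent: Event which remained indefinitely". Section 7.4.1.2.4 records actions taken, including concomitant medication, and then "The outcome and date of outcome according to the following definitions"; one of the outcome categories is "Not recovered or not resolved (adverse event remains without signs of improvement".

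Elsewhere the protocol uses severity in a different sense. The treatment discontinuation list in 4.4.2 includes "Intolerable or persistent adverse events of any severity". Protocol 9.4.7 plans a count of severe events and says that "adverse events of each intensity will be summarized by SOC and preferred term". SAP 17.1 plans TEAEs and serious TEAEs by maximum severity. SAP 17.1.1 names the same three classes without defining them, so the SAP rests on the protocol definition.

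**The concern.** A severity grade is normally read as how intense an event was, or how far it interfered with the patient's life. Here it mostly repeats outcome and treatment, which have their own fields, and no field captures intensity.

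This matters because the trial is meant to support Phase III dose selection (Protocol 1.1) and to examine dose-dependent safety (Protocol 3.2). Protocol 1.2 describes earlier tolerability findings as largely short-lived, for example a transient rise in dizziness that occurred mostly around spirometry or dosing. An event of that kind that passes without treatment is mild by rule, however intense it was. If intensity rose with dose, the tables meant to show it could not.

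**Working it through.** There is no figure to reproduce; the check is to apply the wording to cases. I found no other severity definition in either document.

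In the moderate line I take both qualifiers (specific treatment, no effect on study activities) as applying to the whole line, since the first is what separates it from mild. The severe line has two readings. In reading 1, *with treatment* attaches only to *not tolerated*. In reading 2, it governs both halves.

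| Event | Mild | Moderate | Severe | Result |
|---|---|---|---|---|
| A. Intense, untreated, resolves | Yes | No: not treated | No: resolved, and not treated | Mild |
| B. Trivial, untreated, unresolved | No: unresolved | No: not treated | Reading 1 yes; reading 2 no | Severe, or no grade |
| C. Treated, resolved, tolerated, but affected study activities | No: treated | No: activities affected | No: resolved and tolerated | No grade |
| D. Treated, unresolved, tolerated, activities unaffected | No | Yes | Yes on either reading | Moderate or severe; no precedence rule |

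A does not depend on the reading of the severe line. A looser reading of the moderate line, with *Resolved* standing alone, would let A be mild or moderate and would place C in moderate. It still would not bring in intensity.

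Now set the cases beside the other sections:

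- **Protocol 4.4.2** presumes that a persistent event can have any severity. Under 7.4.1.2.1 an event that never resolves cannot be mild, and without treatment it cannot be moderate.
- **Protocol 9.4.7** calls the grade intensity. Case A shows that the grade does not order events by intensity.
- **SAP 17.1.1** classes a TEAE starting after first dose as severe when its severity is missing. If a site leaves the field blank because no grade fits (C, or B on reading 2), the event is tabulated as severe.

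For reach, SAP 17.1 lists nine TEAE categories for tabulation by SOC and preferred term. Two use the grade: TEAEs by maximum severity and serious TEAEs by maximum severity. The other 9 − 2 = 7 do not: all TEAEs, related, leading to discontinuation, serious, serious related, serious leading to discontinuation, and fatal outcome.

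**The case against.** The best defence is that the definition is not purely outcome and treatment. Tolerability and effect on study activities are functional terms that the outcome and action fields do not hold. That is right, but they enter only for treated events, so they help neither A nor B.

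It is also fair that the consequence is contained. A dose-related rise in the number of short-lived events would still appear in overall TEAE incidence; only the intensity label would mislead. No stopping or dose-selection rule in the documents turns on the grade. I accept this.

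Three stronger readings are tempting but not supported:

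- **That every event open at the follow-up call is severe by rule.** Case D can be moderate, and case B may have no grade. The call is also not a cut-off for outcome: Protocol 7.4.1.3 requires events to be followed until they abate or become stable.
- **That a known share of mild events would move to severe.** The documents give no data on how many events stay open or untreated, so no share can be stated.
- **That the definition breaks the identification of treatment-emergent events.** SAP 17.1 does let a pre-dose event count if its investigator-rated severity worsens. But this concerns only events that begin before the first dose, and the SAP Appendix 2 algorithm classifies events with known start dates by date alone. That mismatch is a separate matter, and intensity grades would not settle it.

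**Conclusion.** The point holds in a limited form. Following Protocol 7.4.1.2.1 as written yields a grade that does not measure intensity, is ambiguous for some events and leaves others without a grade. It conflicts with the use of severity in Protocol 4.4.2 and with the tables in Protocol 9.4.7 and SAP 17.1.

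Affected are the severe-event count and by-intensity summary in Protocol 9.4.7 and two of the nine TEAE tabulations in SAP 17.1. All are descriptive, and the primary endpoint and other efficacy analyses are untouched. The size of the distortion cannot be estimated from the documents. The result for case A needs only that investigators apply the stated definitions; B and C also depend on the readings set out above. If sites graded by intensity out of habit, the tables would be less distorted, but they would then not follow the protocol. The sponsor should correct this; it does not threaten the trial's main conclusion.

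**What to change.** Replace the three definitions with grades of intensity or interference. For example: mild, noticed but no interference with usual activity; moderate, some interference; severe, usual activity prevented. Leave treatment given, chronicity and outcome in their existing fields. Then reconcile Protocol 4.4.2, 7.4.1.2.1 and 9.4.7 with SAP 17.1 and 17.1.1 so that severity has one meaning throughout. This concerns the term only; no change to the discontinuation rule is proposed.

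The wording change to the protocol and eCRF guidance is small and adds no visits. The real cost is timing. The synopsis plans the study for May to November 2019 and the SAP is dated 5 December 2019, so events may already carry grades, and a mid-stream change would mix two scales. There are two ways to handle this:

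- have investigators regrade recorded events before unblinding; or
- keep the grades, footnote the definition on every severity table, and cross-tabulate grade by outcome within treatment group.

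The second is cheaper but cannot recover intensity; it only shows how far the grade follows outcome.

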7.4.1.2.2 Chronicity

Single occasion: Single event with limited duration.

Intermittent: Several episodes of an event, each of limited duration.

Persistent: Event which remained indefinitely.

7.4.1.2.3 Causality

The Investigator will assess causal relationship between the study medication and each adverse event, and answer "yes" or "no" to the question, "Do you consider that there is a reasonable possibility that the event may have been caused by the study medication?"

For SAEs, causal relationship will also be assessed for study procedures, additional study medication, and other medication. Note that for SAEs that could be associated with any study procedure, the causal relationship is implied as "yes".

A guide to the interpretation of the causality question is found in Section 14.3.

7.4.1.2.4 Action and Outcome

- Action taken with study medication (none, study medication stopped, study medication temporarily interrupted)
- Other actions (none, concomitant medication, study discontinuation, hospitalization, other)
- The outcome and date of outcome according to the following definitions:
 - Recovered or resolved (adverse event disappeared)
 - Recovering or resolving (patient is recovering)
 - Not recovered or not resolved (adverse event remains without signs of improvement)
 - Recovered or resolved with sequelae (adverse event has resulted in permanent disability or incapacity)
 - Fatal
 - Unknown (only applicable if patient has been lost to follow-up)

- Seriousness (yes or no)

7.4.1.3 Reporting Procedure for SAEs

The Investigator must report all SAEs to the Sponsor as soon as practical, but in all cases within 24 hours of awareness. Any fatal SAEs notified in the 28-day period after the last dose of study medication must also be reported.

SUSARs will be determined by the Sponsor's Medical Monitor.

SAEs will be reported to the institutional review board(s) and regulatory authority(is) according to local requirements.

All adverse events will be followed until they have abated, or until a stable situation has been reached. Depending on the event, follow up may require additional tests or medical procedures as indicated, and/or referral to the patient's general physician or a medical specialist.

It is the responsibility of the Investigator to ensure that any necessary additional therapeutic measures and follow-up procedures are performed.

7.4.2 Pregnancy

Urine pregnancy tests will also be performed by the study center at Screening (confirmed to be negative prior to the chest X-ray) and pre-dose at Visits 2 and 6.

Should a female patient become pregnant, or if a male patient fathers a child during the study or in the 30 days after the end of the study, the Investigator must be informed immediately. The Investigator will report this information to the Sponsor within 7 days of awareness. The Investigator will make all reasonable efforts to ascertain the progress and outcome of the pregnancy. If the outcome meets the criteria for immediate classification of a SAE (e.g., spontaneous or therapeutic abortion, stillbirth, neonatal death, congenital anomaly, birth defect), the Investigator must follow the procedure for reporting SAEs.

7.4.3 Laboratory Safety Assessments

In addition to the laboratory safety tests detailed below, unscheduled and/or repeat testing may be performed at the discretion of the Investigator. Any additional laboratory results will also be merged into the final database. Laboratory results will be provided to the Investigator for each patient and each visit. The Investigator should assign whether each abnormal result is not clinically significant or a clinically significant by manually annotating a print out of the results.

Samples will be taken and handled according to the manual provided by the central laboratory.

7.4.3.1 Hematology

The following will be measured: hemoglobin, hematocrit, total white cell count, leukocyte differential count and platelet count.

At each time point, a sample of venous blood will be collected in a collection tube containing EDTA.

7.4.3.2 *Blood Chemistry*

The following will be measured: creatinine, total bilirubin, alkaline phosphatase, aspartate aminotransferase, alanine transaminase, gamma-glutamyl transferase, lactate dehydrogenase, creatine kinase, TSH, triiodothyronine, thyroxine, glucose, potassium, sodium and calcium. These assessments will be performed at the same times as for hematology. **Note:** TSH, triiodothyronine and thyroxine will be analyzed for samples obtained at Visit 1 only, to assess for hyperthyroidism, in accordance with Exclusion Criterion 10 and Section 7.1.5.

At each time point, a sample of venous blood will be collected in a vacutainer collection tube.

7.4.3.3 *Urinalysis*

A midstream urine sample will be collected in a sterile container at the same time points as hematology and blood chemistry. The following will be tested: leukocytes, blood, ketones, bilirubin, urobilinogen, protein and glucose. If urinalysis on Dipstick is positive for leukocytes and/or blood/hemoglobin, a microscopic examination including erythrocytes, leukocytes, bacteria, casts, epithelial cells and crystals will be performed.

7.4.4 *Vital Signs*

Blood pressure and pulse rate will be measured at each study visit in accordance with the information provided in Section 6. Post-dose measurements will be taken in relation to the morning dose of RPL554 or placebo.

At each time point, supine vital signs will be assessed while the patient has been at rest for at least 5 minutes.

7.4.5 *Physical Examination*

A full physical examination, covering major body systems (assessments of the nose, throat, skin, thyroid gland, neurological system, respiratory system, cardiovascular system, abdomen [liver and spleen], lymph nodes and extremities) will be performed at Screening (Visit 1) and End of Study (Visit 6). Results will be recorded in the eCRF as normal, abnormal not clinically significant or abnormal clinically significant and abnormal results described..

7.4.6 *12-Lead ECG*

12-lead ECGs will be performed at Visits 1, 2, 3 and 6 in accordance with the information provided in Section 6.

Each 12-lead ECG should be taken after at least 5 minutes in the supine position. An overall assessment (normal, abnormal not clinically significant or abnormal clinically significant) will be recorded in the eCRF by the Investigator. The ECGs will be centrally collected and analyzed.

8 QUALITY ASSURANCE AND QUALITY CONTROL

The study will be conducted in accordance with the current approved protocol, standard operating procedures (SOPs) and all applicable guidelines and requirements (see Section 10).

8.1 Audit and Inspection

The Sponsor, or its designee may conduct a quality assurance audit. An inspection of this study may also be carried out by regulatory authorities at their discretion. Such audits or inspections can occur at any time during or after completion of the study. If an audit or inspection occurs, the Investigator and institution agree to allow the auditor/inspector direct access to all relevant documents and to allocate his time and the time of his staff to the auditor or inspector to discuss findings and any relevant issues.

8.2 Monitoring and Source Document Verification

The study will be monitored by a monitor approved by the Sponsor. During these visits, all procedures will be monitored for compliance with the protocol. Source documents will be reviewed and compared with the data entries in the eCRFs to ensure consistency. The Sponsor will ensure that the study is monitored in accordance with the principles of ICH GCP. The frequency of monitoring visits will be determined, in part, by the rate of patient recruitment.

The following are examples of items that will be reviewed at these visits:

- Compliance with the protocol
- Consent procedure
- Source documents
- Adverse event procedures
- Storage and accountability of materials

The monitoring visits also provide the Sponsor with the opportunity to ensure that timely patient accrual and the other Investigator's obligations and all applicable requirements are being fulfilled.

The Investigator must permit the study monitor, the institutional review board, the Sponsor's auditors and representatives from regulatory authorities direct access to all source documents for confirmation of the accuracy and reliability of data contained within the eCRFs (source document verification). Patient confidentiality will be protected at all times.

Source documents are defined as the results of original observations and activities of a clinical investigation, including medical notes. All source documents produced in this study will be maintained by the Investigator and made available for inspection. The original signed informed consent form for each patient will be retained by the Investigator and the second signed original given to the patient.

Source data include, but is not limited to, the following and will be identified in a source data location log:

- Screening/enrolment log
- Medical notes - which should be updated after each visit to include visit dates, medical history, diagnosis of COPD, concomitant medication, any clinically relevant findings of

- clinical examinations or clinically relevant adverse events/medication changes, SAEs and information on patient withdrawal
- Informed consent form
- 12-lead ECGs
- Laboratory reports
- Visit dates
- Study medication accountability/inventory forms

The study monitor will carry out source document verification at regular intervals. This is an essential element of quality control, as it allows the rectification of transcription errors and omissions.

8.3 Data Management and Coding

Data for each patient will be recorded in an eCRF. Data collection must be completed for each patient who signs an informed consent form and receives at least one dose of study medication.

eCRFs will be designed and produced by the Sponsor or designee and should be completed in accordance with instructions. The Investigator is responsible for maintaining adequate and accurate medical records from which accurate information will be transcribed directly into the eCRFs using a secure internet connection. The eCRFs should be filled out completely by the Investigator or designee as stated on the delegation of responsibilities form. The eCRF system will be Food and Drug Administration Code of Federal Regulations 21 Part 11 compliant.

The eCRFs must be reviewed, signed and dated by the Investigator.

Data entered into the eCRF will be validated as defined in the data validation plan. Validation includes, but is not limited to, validity checks (e.g. range checks), consistency checks and customized checks (logical checks between variables to ensure that study data are accurately reported) for eCRF data and external data. A majority of edit checks will be triggered during data entry and will therefore facilitate efficient 'point of entry' data cleaning.

Data management personnel will perform both manual eCRF review and review of additional electronic edit checks to ensure that the data are complete, consistent and reasonable. The electronic edit checks will run continually throughout the course of the study and the issues will be reviewed manually online to determine what action needs to be taken.

Manual queries may be added to the system by clinical data management or study monitor. Clinical data managers and study monitors are able to remotely and proactively monitor the patient eCRFs to improve data quality.

External data (laboratory safety, 12-lead ECG and PK data) will be transferred electronically into the study database. Discrepancies will be queried to the site and/or the laboratory until the electronic data and the database are reconciled.

All updates to queried data will be made by authorized study center personnel only and all modifications to the database will be recorded in an audit trail. Once all the queries have been resolved, eCRFs will be locked by password protection. Any changes to locked eCRFs will be approved by the Investigator.

Once the full set of eCRFs have been completed and locked, the Sponsor will authorize database lock and all electronic data will be sent to the designated statistician for analysis. Subsequent changes to the database will then only be made only by written agreement of the Sponsor.

Adverse events will be coded from the verbatim description (Investigator term) using the Medical Dictionary for Regulatory Activities. Prior and concomitant medications will be coded according to the World Health Organization drug code. An independent coding review will be performed by the Sponsor.

The clinical database (in Statistical Analysis System [SAS] format) will be transferred to the Sponsor at the end of the study.

